7.3.2 Causality Assessment

The DCC nomenclature for assessing the causal relationship between the study product/procedure and an event is listed in the following table.

Adverse Event/Suspected Adverse Reaction Relationship to Study Product/Procedure

Unrelated	No temporal association to study product/procedure. An alternate etiology has been established.
Unlikely	Clinical events which are likely to be caused by subject's clinical state, environment or administration of other therapies or exposure to toxins.
Possibly related	Reasonable temporal relationship to study product/procedure. Connection to study product/procedure cannot be ruled out.
Probably related	There is a reasonable temporal association with the study product/procedure. There is a high degree of certainty that the event is related to the study product/procedure.
Definitely related	There is a direct temporal relationship to the study product/procedure. The event follows a known pattern of response to the study product/procedure.

The Investigator chooses the category that overall best describes the relationship between the event and the study product/procedure and records the evaluation on the Adverse Event eCRF. Note: If the Investigator does not know whether or not the study product/procedure caused the event, then the event will be handled as “possibly related to investigational product” for reporting purposes.

7.3.3 Expectedness Assessment

The DCC nomenclature for assessing whether an event is expected or unexpected with regard to the study product is listed in the following table.

Expected	Any event for which the nature or severity is consistent with information in study Investigator Brochure
Unexpected	Any event for which the nature or severity is not consistent with information in study Investigator Brochure

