7.4.2 Sponsor Reporting Requirements to the EC, NHLBI and DSMB

Once the event has been reported to the DCC by the Investigator, the DCC uses the Medical Dictionary for Regulatory Activities (MedDRA) System Organ Classification (SOC) to classify all AEs/SARs (including SAEs/SSARs assessed by Investigator or DCC). Additional supporting documentation may be requested from the site Investigator and his/her team to enable the DCC Safety Officer to accurately assess the event for reporting.

Type of SAE/SSAR		Type of Report	Reporting Timeframe
Event is NEITHER grade 3 or higher, NOR unexpected, NOR related	➡	Cumulative DSMB report	Every six months
Event is ONE OF: grade 3 or higher OR unexpected OR related	➡	Email notification to DSMB	Within 15 days
Event is grade 3 AND EITHER unexpected OR related	➡	Email notification to DSMB	Within 15 calendar days
		Event specific report to DSMB	Within 30 calendar days
Event is unexpected AND related AND (grade 2-grade 5)	➡	Email notification to DSMB	Within 72 hrs
		Event specific report to DSMB	Within 7 calendar days

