7.4.3 Sponsor Reporting Requirements to FDA

Once the DCC has been notified of a SAE/SSAR the following are the DCC's reporting requirements to the FDA:

Type of SAE/SSAR	Report to	Timeframe
Fatal or life-threatening, unexpected, and associated with study product/procedure	FDA	MedWatch submitted within 7 calendar days of learning of event
Other SAE/SSARs that are non-fatal or life-threatening but are unexpected and associated with study product/procedure	FDA	MedWatch submitted within 15 calendar days of learning of event

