7.5 Unanticipated Problems (UPs)

An UP is an incident, experience, or outcome that specifically causes increased risk to the study or to its participants which may be of medical or non-medical etiology, and meets the following criteria:

- Unexpected (in terms of nature, severity, or frequency), given (a) the research procedures that are described in the protocol-related documents, such as the IRB-approved research protocol and informed consent document; and (b) the characteristics of the subject population being studied;
- Definitely, probably, or possibly related to participation in the research (i.e., there is a reasonable possibility that the incident, experience, or outcome may have been caused by the procedures or materials involved in the research); and
- Suggests that the research places subjects or others at a greater risk of harm (including physical, psychological, economic, or social harm) than was previously known or recognized.

All UP reporting will follow the same guidelines as noted above for SAE/SSAR reporting, and must include a corrective action plan/measures to prevent recurrence.

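### The expected and unexpected definitions in section 7.3.3 overlap, so a related SAE worse than the brochure describes can be moved to a slower DSMB track and lose its FDA MedWatch report

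*Combined protocol and SAP*

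**What the plan says.** Section 7.3.3 sets out two classes, each judged against the Investigator Brochure. The first class, expected, is defined as "Any event for which the nature or severity is consistent with information in study Investigator Brochure". The second class, unexpected, repeats that sentence with one word added, a negation before *consistent*. The section does not say what to do with an event that fits both.

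The class feeds two reporting tables for SAEs and SSARs.

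- **DSMB (section 7.4.2).** The fastest row is "Event is unexpected AND related AND (grade 2-grade 5"): email within 72 hours, event specific report within 7 calendar days. The row "Event is grade 3 AND EITHER unexpected OR related" gives a 15-day email and a 30-day report. The row "Event is ONE OF: grade 3 or higher OR unexpected OR related" gives a 15-day email only. An event with none of these features goes into the six-monthly cumulative report.
- **FDA (section 7.4.3).** A MedWatch is due within 7 calendar days for the first row, "Fatal or life-threatening, unexpected, and associated with study product/procedure". It is due within 15 calendar days for the second row, which reads "Other SAE/SSARs that are non-fatal or life-threatening but are unexpected and associated with study product/procedure".

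Section 7.5 has a separate test for Unanticipated Problems, beginning "Unexpected (in terms of nature, severity, or frequency), given". It is judged against protocol-related documents and the study population, and it adds a relatedness criterion and a greater-risk criterion.

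**The concern.** Two classes that decide a reporting deadline should be mutually exclusive. Here a listed reaction that turns out worse than the brochure describes has a consistent nature, so it is expected, and an inconsistent severity, so it is unexpected. An unlisted kind of event at a severity consistent with the brochure fits both classes in the same way. A site and the sponsor could classify the same event differently and both be within the protocol.

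The neighbouring section handles doubt better. Under section 7.3.2, an event of unknown causality is treated as possibly related for reporting. Expectedness has no such cautious default.

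At stake is how quickly the DSMB hears of a known reaction in a worse form, and whether an expedited FDA report is made. The trial is first-in-human, and under section 7.6 the sponsor relies on the DSMB to identify what should trigger a halt, modification or termination.

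**Working it through.** The plan has no figure to reproduce. The check is one of logic, followed by a walk through the two reporting tables.

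**Step 1: do the definitions overlap?** Inputs: the two rows of section 7.3.3. Let N mean that nature is consistent with the brochure and S that severity is. As written, Expected = N or S, and Unexpected = not-N or not-S.

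| Nature consistent | Severity consistent | Expected (as written) | Unexpected (as written) | Expected (N and S) |
|---|---|---|---|---|
| yes | yes | yes | no | yes |
| yes | no | **yes** | **yes** | no |
| no | yes | **yes** | **yes** | no |
| no | no | no | yes | no |

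Two of four combinations meet both definitions. If Expected needs N *and* S, and Unexpected is left alone, none of the four meets both and none meets neither.

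**Step 2: what does the label change?** Inputs: the tables in sections 7.4.2 and 7.4.3, which cover SAEs and SSARs only. Assumption: grades 4 and 5 count as fatal or life-threatening for the FDA rows. Where several DSMB rows apply, the fastest is shown. The 15-day email row is first read inclusively, as at least one of its three conditions.

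| Related SAE | DSMB if unexpected | DSMB if expected | FDA if unexpected | FDA if expected |
|---|---|---|---|---|
| Grade 2 | email 72 h, report 7 d | email 15 d, no report | 15 d | none |
| Grade 3 | email 72 h, report 7 d | email 15 d, report 30 d | 15 d | none |
| Grade 4 or 5 | email 72 h, report 7 d | email 15 d, no report | 7 d | none |

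With 72 h = 3 d, the email deadline is later by 15 − 3 = 12 days. At grade 3 the event specific report is later by 30 − 7 = 23 days.

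At grades 4 and 5 the label removes the event specific report, because the 30-day row is written for grade 3 and not for grade 3 or higher. If the 15-day email row instead means exactly one of its conditions, a related grade 4 or 5 event classed as expected meets two of them (grade and relatedness) and falls in no DSMB row at all.

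**Step 3: unrelated SAEs.** Neither FDA row applies under either label. On the inclusive reading, an unrelated grade 2 SAE classed as expected moves from a 15-day email to the six-monthly report. An unrelated grade 3 SAE keeps its 15-day email but loses the 30-day report. Grades 4 and 5 are unchanged.

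**The case against.** The strongest reply is that no reporting row is triggered by the word *expected*. Every expectedness condition in sections 7.4.2 and 7.4.3 is written on *unexpected*, and an event worse than the brochure describes always meets that definition. Read literally, a related event of this kind belongs in the 72-hour row and in an FDA row. Losing them requires someone to let the expected label override, and no section says it should. This stands, and it limits the point: the text allows the slower track but does not direct anyone to it. It does not remove the defect, because section 7.3.3 offers the classes as alternatives and gives no rule for choosing when both fit.

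A reader might infer that these events can be kept out of DSMB reporting altogether, or that the lead-in review would miss them. The documents do not support that. On the inclusive reading, a related SAE still reaches the DSMB by 15-day email. Section 7.6 has the DSMB evaluate all SAEs and SSARs, including their expectedness. Section 7.7 has it review 1-month data from each of the six lead-in subjects whatever the label, and those data also go to FDA.

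There are further backstops. Under section 7.4.1 the email carries the site's view of expectedness and a sponsor assessment. Section 7.4.2 has the DCC Safety Officer assess events for reporting. Section 7.5 may catch a known reaction in a worse form as an Unanticipated Problem. Sections 7.0 and 9.4.4 commit the program to US regulation, so the section 7.4.3 table is not the only FDA obligation. These reduce the consequence, but none restates or corrects the definition. The full sponsor assessment of expectedness sits in the event specific report, which is itself what the label delays or removes.

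**Conclusion.** The overlap is real and unresolved: two of four combinations satisfy both definitions. For a related SAE in the overlap, the expected label downgrades DSMB reporting from 72 hours and 7 days to a 15-day email, with a 30-day report at grade 3 only, and removes the section 7.4.3 MedWatch report. The effect is a delayed or reduced DSMB notice and a lost FDA report. It is permitted, not required, and it is partly covered by other review steps.

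The conclusion rests on three things: a literal reading of the tables; grades 4 and 5 being treated as fatal or life-threatening; and, for the statement that the DSMB is still told, the inclusive reading of the 15-day row. How many events would fall in the overlap cannot be estimated, because that depends on what the Investigator Brochure says about severity. The eCRF is not available either, so whether it forces a single choice is unknown. This is a drafting fault in a safety rule and should be corrected.

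**What to change.** In section 7.3.3, change the expected row so that both the nature *and* the severity must be consistent with the Investigator Brochure. Leave the unexpected row as it stands; it is then the exact complement. Carry the same wording into any eCRF help text. Have the DCC Safety Officer re-check SAEs already recorded as expected and re-classify only those that fail the corrected definition.

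The cost is a small wording change in one table, the matching help text and a short re-check. A few more events will be reported early. Some of these may be milder than the brochure describes, since a milder form is also not consistent with it and would be classed only as unexpected.

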7.4 Reporting Responsibilities of the Sponsor (DCC)

7.4.1 Safety Monitoring Program and Reporting

The Safety Monitoring Program uses a combination of, email notifications, event specific reports, and scheduled cumulative trial reports to keep the NHLBI Program Director and NHLBI DSMB informed about real and potential safety issues.

Email Notifications are comprised of an email to the NHLBI Program Director and NHLBI DSMB Executive Secretary with available information on the date and nature of the event, the site Investigator's evaluation of the severity, expectedness, and relatedness to study product/procedure; and a Sponsor assessment of the event given the information known at the time of the initial reporting.

Event specific reports are formal written reports providing the details of the event (including circumstances surrounding the event, laboratory testing, concomitant medications, and any formal diagnoses made via medical intervention). These reports include a full sponsor assessment of the severity, expectedness, and relatedness to study product/procedure as well as any available status update on the subject.

Scheduled cumulative trial reports are prepared semi-annually by the DCC. These are used by the NHLBI DSMB to assess recruitment, subject safety, and continued trial feasibility. These reports include total numbers of AE/SARs and SAE/SSARs experienced in the overall trial. The information provided includes both new events

reported since the last DSMB meeting and cumulative events reported during the life of the trial.

7.4.2 Sponsor Reporting Requirements to the EC, NHLBI and DSMB

Once the event has been reported to the DCC by the Investigator, the DCC uses the Medical Dictionary for Regulatory Activities (MedDRA) System Organ Classification (SOC) to classify all AEs/SARs (including SAEs/SSARs assessed by Investigator or DCC). Additional supporting documentation may be requested from the site Investigator and his/her team to enable the DCC Safety Officer to accurately assess the event for reporting.

Type of SAE/SSAR		Type of Report	Reporting Timeframe
Event is NEITHER grade 3 or higher, NOR unexpected, NOR related	➡	Cumulative DSMB report	Every six months
Event is ONE OF: grade 3 or higher OR unexpected OR related	➡	Email notification to DSMB	Within 15 days
Event is grade 3 AND EITHER unexpected OR related	➡	Email notification to DSMB	Within 15 calendar days
		Event specific report to DSMB	Within 30 calendar days
Event is unexpected AND related AND (grade 2-grade 5)	➡	Email notification to DSMB	Within 72 hrs
		Event specific report to DSMB	Within 7 calendar days

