7.3.1 Severity Assessment

The DCC uses the Common Terminology Criteria for Adverse Events (CTCAE), version 4.0, for detailed descriptions of Severity Grades. The CTCAE schema is classified by body system and event using the MedDRA hierarchy and provides descriptions of events that qualify under each severity rating.

The following table contains general descriptions of Adverse Event Severity Grades.

Please note: Grade 1 (Mild) AE/SARs are not entered in the electronic CRF in the CCTRN database.

Severity Grade	Description
1	Mild. Asymptomatic or mild symptoms; clinical or diagnostic observations only; intervention is not indicated.
2	Moderate. Minimal, local, or non-invasive intervention indicated or limiting activities of daily living (i.e. preparing meals, shopping for groceries/clothes, managing money, using telephone, etc.)
3	Severe or medically significant but not immediately life-threatening. Hospitalization or prolongation of hospitalization indicated OR disabling OR limiting self-care (e.g. bathing, dressing, feeding self, using toilet, taking medications, etc.)
4	Life-threatening consequences; urgent intervention indicated.
5	Death. Death related to adverse event.

Notice that severity and seriousness are different concepts. For example, a headache may be severe (interferes significantly with subject's usual function) but would not be classified as serious unless it met one of the criteria for SAE/SSARs (see section 7.1.3 above).

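### The third row of the DSMB reporting table (7.4.2) covers grade 3 only, so some grade 4-5 SAEs need no event-specific report although the same events at grade 3 do

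*Combined protocol and SAP*

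**What the plan says.** Section 7.4.2 of the protocol has a four-row table that sets what the sponsor (the DCC) sends to the DSMB for each SAE or SSAR, and when. Counting from the top:

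- Row 1: "Event is NEITHER grade 3 or higher, NOR unexpected, NOR related". These go only into the six-monthly cumulative report.
- Row 2: "Event is ONE OF: grade 3 or higher OR unexpected OR related". Email within 15 days.
- Row 3: "Event is grade 3 AND EITHER unexpected OR related". Email within 15 calendar days and an event-specific report within 30 calendar days.
- Row 4: "Event is unexpected AND related AND (grade 2-grade 5". Email within 72 hours and an event-specific report within 7 calendar days.

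Section 7.4.1 explains the report types: "Event specific reports are formal written reports providing the details of the event". They include the sponsor's full assessment of severity, expectedness and relatedness. The email gives what is known at first reporting, with the investigator's evaluation and a sponsor assessment on that basis. Section 7.3.1 defines grade 4 as life-threatening and grade 5 as death.

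**The concern.** Only rows 3 and 4 call for an event-specific report, and row 3 is the only row whose grade condition is a single grade. Read literally, the written-report requirement rises from grade 2 to grade 3 and then falls at grades 4 and 5. A related, expected event needs a written report if it is severe, but not if it threatens life or kills; the same holds for an unexpected event judged unrelated.

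In Section 7.6 the sponsor relies on the DSMB to identify what should trigger a halt, modification or termination. Section 7.7 sends lead-in events through the same 7.4 rules, and DSMB review of the lead-in must succeed before the randomized part opens. In a first-in-human trial, the table should not guarantee the DSMB less detail on a death than on a grade 3 event with the same attributes.

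Row 2 adds an ambiguity, because it can mean at least one of its three criteria or exactly one. That decides whether the affected events keep an email or match no row.

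**Working it through.** The plan gives no figure to reproduce, so the check puts every type of event through the four rows.

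**Inputs.** Grades 2 to 5; expected or unexpected (7.3.3); related or unrelated (7.3.2). Grade 1 is left out because "Grade 1 (Mild) AE/SARs are not entered in the electronic CRF in the CCTRN database". That gives 4 x 2 x 2 = 16 combinations.

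**Event-specific report required, as written (row 3 or row 4):**

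| Grade | Expected, unrelated | Expected, related | Unexpected, unrelated | Unexpected, related | Required in |
|---|---|---|---|---|---|
| 2 | no | no | no | yes, 7 days | 1 of 4 |
| 3 | no | yes, 30 days | yes, 30 days | yes, 7 days | 3 of 4 |
| 4 | no | **no** | **no** | yes, 7 days | 1 of 4 |
| 5 | no | **no** | **no** | yes, 7 days | 1 of 4 |

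The total is 1 + 3 + 1 + 1 = 6 of 16. The bold cells are the gap: 2 grades x 2 attribute patterns = 4 of 16.

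**What the gap cells do receive.**

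- Row 2 as at least one criterion (the complement of row 1): all four get the 15-day email and lose only the written report. Six of the 16 combinations then match more than one row: grade 2 with both attributes; grade 3 with either or both; grades 4 and 5 with both.
- Row 2 as exactly one criterion: each gap cell meets two criteria, so row 2 does not apply, and neither does any other row. The four combinations that match no row are exactly these four.

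**Does another section close the gap?**

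- 7.4.1 describes the report types but sets no triggers.
- 7.4.3 expedites to the FDA events that are "Fatal or life-threatening, unexpected, and associated with study product/procedure", and other SAEs only if also unexpected and associated. The gap events have one attribute, not both.
- 7.5 likewise needs unexpected and related, and refers back to the same SAE rules.
- 7.6 has the DSMB evaluate all SAEs under its charter, but names no report type or deadline.

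**With the wording proposed below.** Row 1 takes 1 combination, row 2 takes 2 + 1 + 1 + 1 = 5, row 3 takes 3 grades x 2 = 6, and row 4 takes 4. The sum is 1 + 5 + 6 + 4 = 16, each in exactly one row. The written report is required in 1, 3, 3 and 3 of 4 at grades 2 to 5, or 10 of 16.

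**The case against.** The best defence is that this is a slip and readers will see through it. Rows 1 and 2 set the severity criterion at grade 3 or above, so row 3 may be shorthand for that criterion. Row 2 follows a row that means none of the three, so at least one is its natural sense, and the email is then kept on the same 15-day clock as at grade 3. That email already carries a sponsor assessment.

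Other rules shrink the gap. Under 7.3.2, when the investigator does not know the cause, the event is handled as possibly related, so an unexpected event of uncertain cause moves to row 4. Under 7.3.3 an event can be unexpected on severity alone, which may move some fatal or life-threatening related events there too. Section 7.3 requires related events to be followed until resolved or stable, so the information is collected. The DSMB charter may ask for more. Overlapping rows do no harm if the stricter one is applied.

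Much of this stands as a limit on size. Fewer real events fall in the gap than the table suggests, and on the likelier reading the DSMB still hears of them. It does not remove the gap. The shorthand reading is a guess at intent, and the text says otherwise. Sections 7.3.2 and 7.3.3 move some events, not all, and 7.3.3 is itself loose: expected means "Any event for which the nature or severity is consistent with information in study Investigator Brochure", so an event whose nature is listed but whose severity goes beyond the Brochure meets both definitions. Follow-up under 7.3 produces data but no DSMB report. The table has no rule that the stricter row governs an overlap.

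**Conclusion.** The concern holds. As written, 4 of the 16 combinations, all at grade 4 or 5, carry no event-specific report, while the same attributes at grade 3 require one within 30 days. Events both unexpected and related are unaffected at every grade from 2 to 5.

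The loss is the written report alone if row 2 means at least one criterion, and the email as well if it means exactly one. These are cells of a table, not expected event counts. How many procedural complications would be touched depends on what the Investigator Brochure lists as expected. Sections 9.1.2.1 and 9.1.2.3 name perforation, stroke and death as known risks. If the Brochure treats them as expected, which is an assumption, a related procedural death would be a gap case. Neither the Brochure nor the DSMB charter is among the documents, and the charter might require more.

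No endpoint or estimate is affected. It should still be corrected, because following the stated rule gives the DSMB less required detail on the gravest events.

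**What to change.** The sponsor should confirm the intent of row 3 and reconcile it with the other rows. Proposed wording:

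- Row 2: exactly one of grade 3 or higher, unexpected, related.
- Row 3: grade 3 or higher, and either unexpected or related but not both.
- Rows 1 and 4: unchanged.

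Each combination then has one row, no current requirement is lowered, and reporting never decreases as grade rises. Extending row 3 to grade 3 or higher is the essential part and closes the gap on either reading of row 2; the other edits remove the ambiguity and the overlaps.

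The cost is a few words in one table and a few more event-specific reports in a trial of about 36 subjects.
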